11.2.3. Pharmacokinetic and Pharmacodynamic Analysis

All patients who receive at least 1 dose of study drug and have at least 1 quantifiable PK result will be included in the population PK analysis. The data from this study may be combined with other Sponsor SMA studies for both population PK analysis and exposure-response analysis, if data permit. SRK-015 concentrations and circulating latent myostatin concentrations will be determined using blood samples collected before and after dosing through the final follow-up visit. SRK-015 concentrations will be listed and summarized in tabular formats using descriptive statistics and will be plotted against time points by cohort, and dose and schedule. The latent myostatin concentrations will be listed for each patient and summarized by cohort.

11.2.4. Anti-SRK-015 Antibody Analysis

All patients who receive at least 1 dose of study drug and have at least 1 ADA result will be included in the immunogenicity evaluation. The ADA population is defined as patients who receive at least 1 dose of study drug and have a pretreatment result and at least 1 posttreatment result from the ADA sample collection. Immunogenicity will be evaluated through a 3-tier ADA assay (screening, confirmatory, and titer) and a neutralizing antibody assay. The number and percent of patients who become positive for ADAs and who develop neutralizing antibodies will be listed and summarized in tabular format using descriptive statistics by cohort, visit, dose and schedule, and overall.

11.3. Sample Size Rationale

Sample sizes for each cohort were based on practical considerations. Sample sizes of 15 to 20 patients for each cohort will provide 80% power to reject the null hypothesis involving mean changes from Baseline within each treatment group relative to prespecified alternative hypothesis using a paired t-test with two-sided 5% Type 1 error. [Table 8](#) presents the effect sizes within dose groups that can be detected with 80% power and two-sided 5% Type I error as well as the effect sizes that will reject the null hypothesis of no difference according to two-sided $p=0.05$. As illustration, assuming a 2.5-unit standard deviation (SD) for the change from Baseline for HFMSE, a mean 1.7-unit improvement for HFMSE ($n=20$) and a mean 2-unit improvement for HFMSE ($n=15$) can be detected with 80% power while a mean 1.2-unit improvement in HFMSE ($n=20$) and a mean 1.3-unit improvement in HFMSE reaches two-sided $p=0.05$ (rules out a 0 as the two-sided 95% CI for the change from Baseline).

Table 8: Paired T-test: Reject Null Hypothesis No Mean Change from Baseline

	80% Power		Two-sided p=0.05	
Test significance level, α	0.05	0.05	0.05	0.05
Effect size, $e = \Delta_1 - \Delta_2 / s$	0.66	0.778	0.462	0.543
n (after losses)	20	15	20	15

In addition, the total sample size for Cohort 3 (n= 20) provides 80% power to reject the null hypothesis of no mean change from Baseline against the prespecified difference between doses for a clinically meaningful improvement at a two-sided 5% Type I error for a 1:1 randomization (high dose vs. low dose).

Table 9 presents the effect size which could be detected with 80% power and a two-sided 5% Type 1 error as well as the effect sizes required to reject the null hypothesis of no change from Baseline for comparing Cohort 3 low vs. high dose. If the SD of the change from Baseline is 2.5 units for HFMSE, then a mean 2.4-unit difference between low and high dose will reach two-sided p=0.05 (rules out 0 as the lower two-sided 95% CI as the mean difference between dose groups).

Table 9: Unpaired T-test: Reject Null Hypothesis: No Mean Difference from Baseline

	80% Power	Two-sided p=0.05
Two-sided significance level, α	0.05	0.05
Effect size, $e = \Delta_A - \Delta_0 / s$	1.325	0.926
n per group (after losses)	10	10

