- Time to therapeutic effect (described in the statistical analysis plan [SAP]) as compared between low- and high-dose SRK-015 arms

Safety:

Safety will be evaluated based on occurrence of or changes in the following parameters:

- Treatment-emergent adverse events (TEAEs) and SAEs
- Vital signs, including blood pressure, heart rate, body temperature, and respiratory rate
- Height and weight
- Physical examinations
- Laboratory assessments (hematology, serum chemistry, coagulation, urinalysis)
- 12-lead electrocardiogram (ECG)
- Concomitant medications

Safety assessments may be revised if any important safety signals emerge from any ongoing clinical studies (including this study).

Pharmacokinetics, Pharmacodynamics, and Immunogenicity:

Blood samples for the measurement of SRK-015 concentrations, circulating latent myostatin concentrations, and anti-SRK-015 antibodies will be obtained prior to dosing on Day 0 and throughout the Treatment and Extension Periods as well as the Safety Follow-up Period as indicated in the Study Schedule of Assessments.

Sample Size Rationale:

Sample sizes for each cohort were based on practical considerations. Sample sizes for Cohorts 1 (n=20) and Cohort 2 (n=15) each provide 80% power to reject the null hypothesis (expressed as means) relative to prespecified alternative hypothesis using a paired t-test with two-sided 5% Type I error for the mean change from Baseline for predefined cohort-specific primary efficacy endpoints. For Cohort 3 (n=20), the effect size to compare dose groups is also justified for detection with 80% power and two-sided 5% Type I error for a 1:1 randomization (high dose versus low dose) as well as the treatment-specific effect sizes that will reject the null hypothesis of no mean difference according to two-sided testing for a predefined primary efficacy endpoint.

Statistical Methods:

Safety and efficacy endpoints will be separately analyzed by cohorts and within Cohort 3, by dose groups. The safety and efficacy endpoints will also be analyzed for different cohort/dose combinations taking cohort, dose level and receiving background SMA therapy into consideration. Any changes in the analysis as specified in the protocol will be delineated in the SAP.

Vital signs and laboratory outcomes will be summarized within each treatment group within all cohorts and the 2 dose groups within Cohort 3. The incidence rate of AEs and TEAEs will be reported.

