9.1.1.6. Hammersmith Functional Motor Scale Expanded

The HFMSE assesses the physical abilities of patients with Type 2 and Type 3 SMA (O'Hagen 2007; Glanzman 2011) and will be performed for nonambulatory patient subgroups (Cohorts 2 and 3). It consists of 33 items graded on a scale of 0, 1, 2, where 0 denotes unable, 1 denotes performed with modification or adaptation, and 2 denotes without modification or adaptation.

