2.2.3 Sample Size Determination

Sample sizes for each cohort were based on practical considerations. The following calculations are to illustrate some scenarios of the power yield by the chosen sample size with certain effect size assumptions.

Sample sizes of 15-20 patients for each cohort will provide 80% power to reject the null hypothesis involving mean changes from Baseline within each treatment group relative to prespecified alternative hypothesis using a paired t-test with 2 sided 5% Type I error. [Table 1](#) presents the effect sizes within dose groups that can be detected with 80% power and two-sided 5% Type I error as well as the effect sizes that will reject the null hypothesis of no difference according to two-sided $p=0.05$. As an illustration, assuming a 2.5 unit standard deviation for the change from Baseline for Hammersmith Functional Motor Scale Expanded (HFMSE), a mean 1.7-unit improvement for HFMSE ($n=20$) and a mean 2-unit improvement for HFMSE ($n=15$) can be detected with 80% power while a mean 1.2 unit improvement in HFMSE ($n=20$) and a mean 1.3-unit improvement in HFMSE reaches two-sided $p=0.05$ (rules out a 0 as the two-sided 95% confidence interval [CI] for the change from Baseline).

Table 1: Paired T-test: Reject Null Hypothesis No Mean Change from Baseline

	80% Power		Two-sided $p=0.05$	
Test significance level, α	0.05	0.05	0.05	0.05
Effect size, $e = \Delta_1 - \Delta_2 / s$	0.66	0.778	0.462	0.543
n (after losses)	20	15	20	15

In addition, the total sample size for Cohort 3 ($n=20$) provides 80% power to reject the null hypothesis of no mean change from Baseline against the prespecified difference between doses for a clinically meaningful improvement at a two-sided 5% Type I error for a 1:1 randomization (high dose vs. low dose).

[Table 2](#) presents the effect size which could be detected with 80% power and a two-sided 5% Type I error as well as the effect sizes required to reject the null hypothesis of no change from Baseline for comparing Cohort 3 low vs. high dose. If the standard deviation of the change from Baseline is 2.5 units for HFMSE, then a mean 2.4-unit difference between low and high dose will reach two-sided $p=0.05$ (rules out 0 as the lower two-sided 95% CI as the mean difference between dose groups).

Table 2: Unpaired T-Test: Reject Null Hypothesis: No Mean Difference from Baseline

	80% Power	Two-sided p=0.05
Two-sided significance level, α	0.05	0.05

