3.4.3 Cohort 3: Low Dose and High Dose

3.4.3.1 Primary Efficacy Analyses

The primary efficacy endpoint is the change from Baseline to Day 364 (V15) in HFMSE total score in the high-dose arm. This analysis will also be performed to evaluate the low-dose arm as well as the entire Cohort 3 in total (i.e., high-dose arm and low-dose arm pooled together).

The difference in the change from Baseline in HFMSE total score will also be explored using descriptive statistics and the corresponding 95% CI based on the Student's t-distribution will be reported.

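### The 1.3-unit HFMSE change said to reach p=0.05 gives p=0.064 at n=15, and no within-arm effect size is printed for the Cohort 3 arms of 10

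*Combined protocol and SAP*

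**What the plan says.** Protocol 11.3 and SAP 2.2.3 carry nearly the same text. Groups of 15 to 20 "will provide 80% power to reject the null hypothesis involving mean changes from Baseline within each treatment group", by a paired t-test at two-sided 5%. The table that follows (Protocol Table 8, SAP Table 1) "presents the effect sizes within dose groups that can be detected with 80% power". It has columns for n=20 and n=15 only: 0.66 and 0.778 SD for 80% power, and 0.462 and 0.543 SD for two-sided p=0.05.

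The worked example takes an SD of 2.5 HFMSE units. It gives 1.7 units (n=20) and 2 units (n=15) for 80% power. For significance it gives 1.2 units (n=20), "and a mean 1.3-unit improvement in HFMSE reaches two-sided" p=0.05. That last figure has no n beside it. The text explains p=0.05 as a two-sided 95% CI that rules out zero.

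Cohort 3 has 20 patients randomized 1:1, so 10 per arm. Protocol Table 7 names no arm for its primary endpoint. SAP 3.4.3.1 does: "The primary efficacy endpoint is the change from Baseline to Day 364 (V15) in HFMSE total score in the high-dose arm". The SAP adds that "This analysis will also be performed to evaluate the low-dose arm as well as the entire Cohort 3 in total". For Cohort 3 the protocol synopsis says the between-dose effect size is justified "as well as the treatment-specific effect sizes that will reject the null hypothesis of no mean difference according to two-sided testing".

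On status, SAP 2.2.3 introduces the section with "The following calculations are to illustrate some scenarios of the power yield by the chosen sample size". SAP 3.1.5 and SAP 6 state that no formal testing will be done.

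**The concern.** There are two faults in one short section.

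First, a figure labelled as reaching p=0.05 and excluding zero does neither at the sample size it appears to belong to. The same figure stands in both documents.

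Second, the wording presents the paired figures as holding within each treatment or dose group. Cohort 3 is the only cohort with two dose groups, and neither n in the table is the size of one of its arms. The arm that the SAP makes primary therefore has no stated within-arm detectable effect. The n=10 that does appear, in Protocol Table 9 / SAP Table 2, belongs to the unpaired comparison of the two doses.

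What is at stake is the stated rationale and the precision a reader would expect. A reader who applied the n=20 column to the high-dose arm would expect a much tighter estimate than 10 patients can give.

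**Working it through.** **Inputs.** Paired (one-sample) t-test, two-sided 5%, SD of change 2.5 units, and the table cells above: Protocol 11.3 and SAP 2.2.3. Ten patients per Cohort 3 arm: 1:1 randomization of 20 (Protocol 6.2), and Protocol Table 9. The n=15 for the 1.3-unit figure is inferred. The sentence pairs n=20 with n=15 for power, gives 1.2 to n=20, and the table has only those two sizes.

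**Formulas.** t = mean / (SD/√n) with n−1 df. Smallest significant mean = t(0.975, n−1) × SD/√n. The 80%-power effect size comes from the noncentral t.

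**1. The plan's own figures that reproduce**
- 80%-power effect sizes: 0.660 (n=20), 0.778 (n=15), and 1.325 for the unpaired comparison with 10 per arm. All match.
- 0.660 × 2.5 = 1.65 and 0.778 × 2.5 = 1.95. The printed 1.7 and 2 are safe roundings, with 82% power each.
- 1.2 units at n=20: t = 1.2/(2.5/√20) = 2.147, p = 0.045. This holds.
- 2.4 units between doses: p = 0.046. This holds.

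**2. The figure that does not**
- 1.3 units at n=15: t = 1.3/(2.5/√15) = 2.014 on 14 df, p = 0.064, 95% CI -0.08 to 2.68.
- Threshold: 2.145/√15 = 0.554 SD; × 2.5 = 1.38 units.
- 1.4 units at n=15: t = 2.169, p = 0.048, 95% CI 0.02 to 2.78.

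**3. Other routes to 1.3**
- The table's n=15 cell: 0.543 × 2.5 = 1.36, which rounds to 1.4.
- A normal critical value gives 1.27 at n=15, but 1.10 at n=20, where 1.2 is printed. It is also not the stated test.
- n=20 with 1.3 gives p = 0.031, but 1.2 is already the n=20 figure.
- At SD 2.5, 1.3 needs n of at least 17 (p = 0.048; n=16 gives 0.055). At n=15 it needs an SD of at most 2.34.

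**4. One Cohort 3 arm, n=10**

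| Quantity | SD units | HFMSE units (× 2.5) |
|---|---|---|
| 80% power | 0.996 | 2.49 |
| p=0.05 threshold, 2.262/√10 | 0.715 | 1.79 |

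For comparison, a true effect of 0.66 SD has 46% power at n=10, and 0.778 SD has 59%.

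**5. What the p=0.05 cells are.** The printed 0.462, 0.543 and (unpaired) 0.926 match the effects that have 50% power: 0.462, 0.5435 and 0.926. The exact critical values are slightly larger: 0.468, 0.554 and 0.940. Taken as observed effects, the printed cells give p of 0.053, 0.054 and 0.053. On the 50%-power convention an n=10 cell would be 0.694 (p = 0.056), not 0.715.

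**The case against.** The case against giving this weight is strong, and most of it stands.

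The 1.3 is a slip in one illustrative sentence. It lies 0.06 units below the adjacent table cell (1.36) and 0.08 below the exact threshold (1.38), and a reader can recover the right figure from the table. That limits the harm. It does not make the printed statement true.

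A reader might infer that the plan promises 80% power at 0.66 or 0.778 SD in an arm of 10. The documents do not say so. The opening sentence is limited to groups of 15 to 20, the columns are labelled 20 and 15, and the synopsis attaches the paired 80% claim to Cohorts 1 and 2. The 46% and 59% figures show only what would follow from carrying the columns over to an arm. What remains is loose wording about treatment and dose groups, and a synopsis reference to treatment-specific effect sizes for Cohort 3 with no n=10 value behind it.

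A reader might also think the n=20 HFMSE illustrations are wrong, because Cohort 1 is assessed on the RHS and Cohort 2 has 15 patients. They are not. SAP 3.4.3.1 plans a pooled Cohort 3 analysis on HFMSE, with n=20. Naming that population would help, but its absence is a labelling preference, not an error.

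Finally, the rationale is now historical. Protocol 6.2 reports the 6-month interim results and a 12-month database lock on 19 January 2021. A new detectable-effect value cannot inform planning and could be mistaken for a prespecified one unless it is dated.

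**Conclusion.** Both parts hold, at minor severity. At SD 2.5 and n=15, 1.3 units does not reach two-sided p=0.05; to one decimal the figure should be 1.4. The paired figures are described as within-group, yet no value is given for a group of 10, the size of each Cohort 3 arm and of the arm that the SAP makes primary.

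The first part rests on reading n=15 from context; no other n fits the sentence and the table. The second rests on 10 patients per arm, as planned. The unit values rest on the documents' SD of 2.5; the SD-unit values do not.

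The tempting stronger conclusion is that Cohort 3 is undersized or its analysis compromised. The documents do not support it. The sizes were set on practical considerations, the calculations are offered as illustrations, and the efficacy analyses are descriptive with 95% CIs. No enrolment number, analysis or decision rule uses these figures.

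**What to change.** In Protocol 11.3 and SAP 2.2.3, with no change in enrolment:

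1. Change 1.3 to 1.4 and attach n=15.
2. Limit the paired-test 80% statement to groups of 20 and 15. State separately that in one Cohort 3 arm (n=10) 80% power needs 0.996 SD (2.5 units) and p=0.05 needs 0.715 SD (1.8 units).
3. If the n=10 value goes into the table, put the whole p=0.05 row on the exact critical-value definition: 0.468 (n=20), 0.554 (n=15) and 0.715 (n=10), with 0.940 in Protocol Table 9 / SAP Table 2. Adding 0.715 beside the present 0.462 and 0.543 would mix two definitions in one row.
4. Mark the edits as a dated correction made after the 12-month database lock, so that the n=10 values are not read as prespecified.

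The cost is a few lines of text and, if step 3 is taken, one table row and one cell in each document. Conduct and planned analyses are unaffected. The within-arm figures for Cohort 3 will look less favourable than the n=20 column.

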11.4. Interim Analyses

11.4.1. Pharmacokinetic and Pharmacodynamic Interim Analysis

Prespecified interim analyses to initially evaluate drug exposure (i.e., PK) and target engagement (i.e., PD) in patients with SMA will be conducted. For Cohorts 1 and 2, these analyses will be conducted after approximately 4 patients in each cohort have received at least 2 doses of SRK-015. For Cohort 3, these analyses will be conducted after approximately 6 patients have received at least 2 doses of SRK-015. Data from multiple cohorts may be combined as necessary. Enrollment will continue while the interim analysis is ongoing. Based on these results, and taking into consideration any available safety data, the cohort-specific dose levels may be adjusted. Any adjustment in dose level will not change the frequency of dosing (i.e., every 4 weeks) and the highest dose will not exceed 30 mg/kg, as tested in the Phase 1 study.

11.4.2. Safety and Efficacy Interim Analyses

Prespecified interim analyses to evaluate the initial safety and efficacy of SRK-015 in patients with SMA will be conducted when all enrolled patients complete Day 168 (Visit 8) or are terminated from the study. Interim analyses will be performed on the efficacy endpoints in addition to all safety outcomes and available PK and PD results. Safety data at all visits and efficacy endpoints at Day 168 (Visit 8) will be included in this analysis.

These interim analyses are being conducted to explore the possibility that clinically meaningful effects may be observed early in the course of SRK-015 treatment. Based on the interim results, these insights may inform and expedite the planning of future clinical studies in SMA.

13. DIRECT ACCESS TO SOURCE DATA/DOCUMENTS

13.1. Study Monitoring

This study will be performed in accordance with regulatory requirements outlined in Food and Drug Administration (FDA) 21 CFR Part 50, 21 CFR Part 54, 21 CFR Part 56, 21 CFR Part 312 and 21 CFR Part 11, as well as the ICH GCP E6 Guidelines. A Study Monitor designated by the Sponsor will carefully monitor all aspects of the study for compliance with GCP, SOPs, and applicable government regulations. The Study Monitor will meet with the Investigator and staff shortly before the start of the study to review the procedures for study conduct and documentation. During the study, the Study Monitor will visit the site to verify record keeping and adherence to the protocol.

The Investigator must prepare and maintain adequate and accurate records of all observations and other data pertinent to the clinical study for each study patient. Frequent communication between the clinical site and the Sponsor/designee is essential to ensure that the safety of the study is monitored adequately. The Investigator will make all appropriate safety assessments on an ongoing basis. The Sponsor's medical representative may review safety information as it becomes available throughout the study.

13.2. Audits and Inspections

The Investigator should immediately notify the Sponsor representative of any announced or unannounced regulatory agency inspections. An auditing inspection may also be conducted by the Sponsor representative.

The Investigator will allow Sponsor representatives, contract designees, authorized regulatory authority inspectors, and the IRB/IEC to have direct access to all documents pertaining to the study.

13.3. Institutional Review Board/Independent Ethics Committee

The Investigator must obtain IRB/IEC approval for the investigation. Initial IRB/IEC approval and all materials approved by the IRB/IEC for this study, including the patient consent form and recruitment materials, must be maintained by the Investigator and made available for inspection.

14. QUALITY CONTROL AND QUALITY ASSURANCE

An electronic data system will be used to ensure quality assurance and facilitate data capture during the study. The system is fully CFR 21 Part 11-compliant and provides for control and capture of study operations performance in real time.

The Investigator or a qualified designee will prepare and maintain adequate and accurate study documents (medical records, ECGs, AE and concomitant medication reporting, raw data collection forms, etc.) designed to record all observations and other pertinent data for each patient receiving randomized study drug. The Investigator will ensure the accuracy, completeness, and timeliness of the data reported to the Sponsor and will cooperate with the Sponsor's representative(s) for the periodic review of study documents to ensure the accuracy and completeness of the data capture system at each scheduled monitoring visit. Access to all source documentation will be made available for monitoring and audit purposes. Monitors will conduct 100% source document verification by comparing the eCRFs with the source documents to ensure consistency. Edit check programs, other forms of electronic validation, manual listings, and a query process will be executed to verify the accuracy of the database. The EDC system will maintain a full audit trail of electronic data changes. This information will be provided to the site by means of electronic or manual queries. Only enrolled patients will be entered into the database.

15. ETHICS

15.1. Ethics Review

The protocol and all protocol amendments must be signed and dated by the Investigator and approved in writing by the IRB/IEC in accordance with GCP prior to implementation. In addition, the IRB/IEC must approve the written informed consent and assent forms, any consent or assent form updates, patient recruitment procedures (e.g., advertisements), and any written information to be provided to patients prior to implementation. The Investigator must provide updates to the IRB/IEC with progress reports at appropriate intervals and a Study Progress Report following the completion, termination, or discontinuation of the Investigator's participation in the study.

